4.0 Sample Size

An estimated 63 subjects (both eyes) per treatment arm are planned (Phase I: 12 subjects / Phase II: 114 subjects).

[figure not shown]

Figure 1. Suggested workflow. ITT: Intention-to-treat population; PP: Per-protocol population.

5.0 Sample Size Calculation

For the sample size calculation, changes in the OSDI (*Ocular Surface Dehydration Index*) questionnaire score were considered, in studies with ocular lubricants in patients with dry eye disease (DED), as the primary efficacy variable.

PRO-176 (Nanodrop®; Laboratorios Sophia, SA de CV) is expected to be non-inferior to its comparator (Systane® Balance; Alcon Research Ltd, Fort Worth, TX, USA), according to the following working hypotheses:

$$H_0: \varepsilon \leq \delta$$

$$H_1: \varepsilon > \delta$$

Where $\mu_A - \mu_B = \varepsilon$, is the true difference in means between the test treatment (PRO-176) and the active control (Systane® Balance). Where δ is the non-inferiority margin, and the ratio of the sample sizes between the two groups is given by:

$$k = \frac{n_A}{n_B}$$

Calculations were performed using the non-inferiority equation for two means and for statistical power (Chow et al., 2008).

$$n_A = kn_B \text{ y } n_B = \left(1 + \frac{1}{k}\right) \left(\sigma \frac{z_{1-\alpha} + z_{1-\beta}}{\mu_A - \mu_B - \delta} \right)^2$$

$$1 - \beta = \theta(z - z_{1-\alpha}) + \theta(-z - z_{1-\alpha}) , \quad z = \frac{\pi_A - \pi_B - \delta}{\sigma \sqrt{\frac{1}{n_A} + \frac{1}{n_B}}}$$

Where σ is the standard deviation, $k=nA/nB$ is the agreement ratio, θ is the standard Normal distribution function, α is the type I error (confidence interval), β is the type II error (meaning that $1-\beta$ corresponds to the power) and δ is the test margin.

With a power of 80% ($\beta=0.20$), a significance level of 0.05 (α) and a non-inferiority margin (δ) of -5 points on the OSDI score (Grubbs et al., 2014; Labetoulle et al., 2017; Pérez-Balbuena et al, 2016).

The calculation was based on the study by Benitez-Del-Castillo et al., 2016. Phase I and II clinical study. A total of 156 healthy subjects and patients with DED were enrolled. The Phase I study included 30 healthy volunteers; it was a single-center, parallel-group, open-label study. Phase II was a multicenter, double-blind study. In Phase I, SYL1001 was administered at 1.125% and 2.25% doses, and in Phase II, at 0.375% and 0.75%. After 10 days of treatment, the primary efficacy variable was the effect on the OSDI score. OSDI scores were significantly reduced compared to baseline ($p<0.01$) for all treatments in both Phase I and Phase II. No statistical differences were observed between treatments.

The sample size calculation was performed considering a reduction in the OSDI score of 17.6 points for the placebo group at their final visit versus a reduction of 16.5 points for the treated group. Considering a δ of 17.1, a similar reduction in the OSDI score is expected for both treatments, with no statistically significant differences at their final visit.

The calculation was performed using the online tool: <http://powerandsamplesize.com>.

The estimated sample size was 101 subjects (51 subjects per arm), which was increased by 25% to account for potential losses (25 subjects). The estimated number of subjects (both eyes) was 126.

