
 
- Nanodrop®. Propilenglicol 0.6%. Emulsión oftálmica.Laboratorios Sophia, S.A. de C.V.
 
- Posology:mínima a cumplir de 1 gota 4 veces al día, ambos ojos.
 
- Route of administration:Oftálmica.
 
	
Comparator product, dose and route of administration:	

 
- Systane® Balance. Propilenglicol 0.6%. Emulsión oftálmica.Alcon Laboratories, Inc.
 
- Posology:mínima a cumplir de 1 gota 4 veces al día, ambos ojos.
 
- Route of administration:Oftálmica.
 
	
Duration of treatment:	Approximate duration of the subject in the study:
28 días	35days
Evaluation criteria:	
Efficacy variables:	
Primary efficacy outcome variable:	

 
○ OSDI Test Score (Evaluation Time [ET]: day 29).
 
	
Secondary efficacy outcome variables:	

 
○ Changes in best corrected visual acuity (BCVA) (TE: day 8 and 29).
 
○ Changes in fluorescein tear film break-up time (TRPL) (TE: day 8 and 29)
 
○ Corneal fluorescein staining changes (TE: day 8 and 29).
 
○ Changes in conjunctival staining with lissamine green (TE: day 8 and 29).
 
	
Security variables:	
Primary safety outcome variable:	

 
○ Incidence of unexpected AEs related to the PI (TE: day 8 and 29).
 
	
Secondary safety outcome variable:	

 
○ Incidence of expected AEs (TE day 8 and 29)
 
	
Exploratory outcome variable:	

 
○ Average number of applications performed daily
 
	
Statistical methodology:	
Data will be expressed as measures of central tendency: mean, standard deviation, and ranges for quantitative variables. Qualitative variables will be presented as frequencies and percentages. Statistical analysis will be performed using the Student t test or the Mann-Whitney U test (if	

applicable) for quantitative variables to determine the difference between groups. Differences between qualitative variables will be analyzed using the  $X^2$  (Chi-square) test or Fisher's exact test. A 95% CI will be considered for non-inferiority criteria based on the study objectives, with an  $\alpha < 0.05$  considered significant.

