### 3.4.2 Efficacy hypothesis

$H_0$  = Nanodrop® is inferior to Systane® Balance by more than 5 points on the OSDI test score

$$H_0: \mu_A - \mu_B > \delta$$

$H_1$  = Nanodrop® is inferior to Systane® Balance by 5 points or less on the OSDI test score

$$H_1: \mu_A - \mu_B \leq \delta$$

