## 7.4 Outcome variables

### 7.4.1 Primary outcome variables

- OSDI Test Score (TE: Day 29)
- Incidence of unexpected AEs related to the PI (TE: day 8 and 29)

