## 7.4.4 Definition of variables, methods and scales to be used for measurement

Variable	Guy	Unit (symbol)	Measurement method	Normal value	Evaluation time	Statistical test
Primary outcome						
OSDI	Discreet	Points (-)	Questionnaire	< 13	VB and VF	Mann-Whitney U
Unexpected EAs related to PI	Discreet	Number of cases (n)	Counting	0	VB, V1 and VF	Mann-Whitney U
Unexpected AEs related to the PI (bis)	Nominal categorical	Present/absent (-)	Observation	Absent	VB, V1 and VF	$\chi^2$ or Fisher's exact test
Of secondary outcome						
MAVC	Discreet	Fraction (-)	Snellen chart	1	VB, V1 and VF	Mann-Whitney U
TRPL with fluorescein	Continue	Seconds (s)	Direct observation with slit lamp and blue filter	>10s	VB, V1 and VF	Mann-Whitney U
Corneal staining with fluorescein	Ordinal	Degrees (-)	Direct observation with a slit lamp on the Oxford scale	0	VB, V1 and VF	$\chi^2$ or Fisher's exact test
Conjunctival staining with lissamine green	Ordinal	Degrees (-)	Direct observation with slit lamp and cobalt blue filter, Oxford scale graduation	0	VB, V1 and VF	$\chi^2$ or Fisher's exact test
EA	Discreet	Number of cases (n)	Counting	0	VB, V1 and VF	Mann-Whitney U
EA (repeat)	Nominal categorical	Present/absent (-)	Observation	Absent	VB, V1 and VF	$\chi^2$ or Fisher's exact
Exploratory						
Number of applications made daily	Discreet	Number of applications (n)	Count by Subject's Diary	>4	V1 and VF	Mann-Whitney U

**Table 2**Operational definition of variables

The variables, method, and scales for their measurement are described in detail below. They are listed in order according to **Table 2**

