#### 10.2.2 Justification of the sample calculation

For the sample size calculation, studies with ocular lubricants in patients with dry eye were considered, in which changes in the OSDI score were the primary outcome variable.

Nanodrop® is expected to be non-inferior to its comparator (Systane® Balance), based on the following working hypotheses:

$$H_0: \varepsilon > \delta$$

$$H_0: \varepsilon \leq \delta$$

Where  $\mu_A - \mu_B = \varepsilon$  is the true difference in means between the test treatment (PRO-176) and the active control (Systane® Balance). Where  $\delta$  is the non-inferiority margin, and the ratio of the sample sizes between the two groups is given by:

$$k = \frac{n_A}{n_B}$$

Calculations were performed using non-inferiority equations for two means and for statistical power. [48, 49]

$$n_A = kn_B \text{ y } n_B = \left(1 + \frac{1}{k}\right) \left(\sigma \frac{z_{1-\alpha} + z_{1-\beta}}{\mu_A - \mu_B - \delta}\right)^2$$

$$1 - \beta = \theta(z - z_{1-\alpha}) + \theta(-z - z_{1-\alpha}) , z = \frac{\pi_A - \pi_B - \delta}{\sigma \sqrt{\frac{1}{n_A} + \frac{1}{n_B}}}$$

Where;  $\sigma$  is the standard deviation,  $k = n_A / n_B$  is the coincidence ratio,  $\theta$  is the standard Normal distribution function,  $\alpha$  is the type I error (confidence interval),  $\beta$  is the type II error (meaning that  $1-\beta$  corresponds to the power) and  $\delta$  is the test margin.

With a power of 80% ( $\beta=0.20$ ), a significance level of 0.05 ( $\alpha$ ) and a non-inferiority margin ( $\delta$ ) of -5 points on the OSDI score.

The sample size calculation was performed considering a reduction in the OSDI score of 17.6 points for the placebo group at their final visit versus a reduction of 16.5 points for the treated group. Considering a  $\sigma$  of 17.1, a similar reduction in the OSDI score is expected for both treatments, with no statistically significant differences at their final visit. [50, 51, 52, 53]

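### Protocol and SAP print opposite non-inferiority inequalities for the same OSDI difference, with a -5 margin that does not fit the declared endpoint and no confidence bound named

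*SAP*

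**What the plan says.** **Hypotheses.** Protocol 1.1 and 3.4.2 print the alternative as "H_1: \mu_A - \mu_B \leq \delta" and put it in words as inferiority "by 5 points or less on the OSDI test score". Protocol 10.2.2 repeats that inequality with ε = μ_A − μ_B (Nanodrop minus Systane Balance), but labels both lines H0. SAP 5.0 defines ε identically and prints the reverse: H0 is ε ≤ δ and H1 is ε > δ. SAP 8.0 states that section 5.0 was among the parts changed to agree with the current protocol.

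**Margin and scale.** Protocol 10.2.2 sets a margin "of -5 points on the OSDI score", and SAP 5.0 likewise gives a "non-inferiority margin (δ) of -5 points on the OSDI score". Both base the calculation on reductions in OSDI of 17.6 and 16.5 points.

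**Endpoint.** The Protocol 1.1 synopsis gives "OSDI Test Score (Evaluation Time [ET]: day 29" and Protocol 7.4.1 gives "OSDI Test Score (TE: Day 29". SAP 6.0 also names the score, not its change. Protocol 7.4.4.1 scores more frequent symptoms higher and treats a large rise as lack of efficacy, so higher is worse.

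**Analysis.** The synopsis says: "A 95% CI will be considered for non-inferiority criteria based on the study objectives". Protocol 10.1.2 and SAP 7.0 say much the same. None of the three names a bound or calls the interval one- or two-sided. All three allow a Student t-test or a Mann-Whitney test, but Protocol Table 2 (7.4.4) gives OSDI only "Mann-Whitney U". SAP 7.0 then calls the product safe and effective when the primary outcomes show neither clinical nor statistical differences from the comparator.

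**The concern.** With one ε and one δ, each document's alternative is the other's null. The sign of the margin does not settle which is meant, because -5 suits a difference in reductions while the declared endpoint is the score. The analysis sections could have resolved this by naming the bound and the value it must clear, but they do not. A Mann-Whitney test gives no interval for a mean difference to set against 5 points. The success sentence in SAP 7.0 rewards a non-significant result, which becomes easier to obtain as the data become less precise. At stake is the rule that decides the primary efficacy claim.

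**Working it through.** **Step 1. Which combinations are coherent?** ε is Nanodrop minus Systane Balance throughout.

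| Scale of ε | Worse means | Valid alternative for a 5-point margin | Deciding limit |
|---|---|---|---|
| Final OSDI score (declared) | ε positive | ε < +5 | upper limit below +5 |
| Reduction in OSDI (sample size) | ε negative | ε > −5 | lower limit above −5 |

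The protocol's wording and inequality fit the first row, but only with δ = +5. The SAP's inequality and margin fit the second row, but not the endpoint in SAP 6.0. Protocol 10.2.2 pairs the first row's inequality with the second row's margin and fits neither.

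**Step 2. The plan's own sample size.** Both documents give n per arm = 2 × [σ(z₁₋α + z₁₋β)/(ε − δ)]² for equal arms, with α = 0.05, power 80% and σ = 17.1 (the protocol prints σ; SAP 5.0 prints δ for the same figure). On reductions, taking the treated group as Nanodrop, ε = 16.5 − 17.6 = −1.1 and ε − δ = −1.1 + 5 = 3.9:

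- n = 2 × [17.1 × (1.645 + 0.842)/3.9]² ≈ 238 per arm.
- With a true difference of 0 (distance 5), n is 145 per arm. If the 1.1 points favour Nanodrop (distance 6.1), n is 98 per arm.

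The stated 51 per arm does not reproduce from any of these, so the calculation cannot show which scale and sign were used. The formula uses z₁₋α with α = 0.05, which is one-sided 0.05. The limit of a two-sided 95% CI is one-sided 0.025.

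**Step 3. What the sign does to the decision (illustration).** Assumptions: SD 17.1 for final scores as well as reductions, 51 evaluable per arm (Protocol 10.1.4, SAP 5.0), normal approximation, two-sided 95% CI.

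SE = 17.1 × √(2/51) = 3.386. Half-width = 1.96 × 3.386 = 6.637.

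- *Correct rule on scores (upper limit < +5), true ε = +5:* probability of passing is 0.025.
- *SAP inequality with −5 on scores:* passes if the estimate exceeds −5 + 6.637 = 1.637. At true ε = +5, Φ((5 − 1.637)/3.386) = 0.84.
- *The same, also requiring no statistical difference in OSDI:* P(1.637 < estimate < 6.637) = 0.53.
- *No statistical difference in OSDI alone (z test):* P(−6.637 < estimate < 6.637) at true ε = +5 is 0.69.
- *Protocol inequality with −5 on scores:* passes if the estimate is below −5 − 6.637 = −11.637. For two identical products, Φ(−11.637/3.386) ≈ 0.0003.
- *SAP inequality with −5 on reductions, true ε = −5:* 0.025, so this form is valid on that scale.

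If the bound is one-sided 0.05, the half-width is 1.645 × 3.386 = 5.570. The correct rule then passes 0.05 at the margin, and 0.84 and 0.53 become 0.90 and 0.59.

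At 63 per arm (SE 3.047, two-sided 95%), 0.84 and 0.53 become 0.91 and 0.53.

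Figures that use the SAP 7.0 sentence leave out its safety part and its undefined clinical part, so they are upper bounds.

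**The case against.** The best defence is that the intent is plain. The margin and its direction stand in words in Protocol 1.1 and 3.4.2, the synopsis ties the CI to the study objectives, and each document can be read coherently alone: the protocol with +5 on the score, the SAP with −5 on reductions. The duplicate H0 in Protocol 10.2.2 is a labelling slip, since 1.1 and 3.4.2 label the lines correctly. The t-test route in the synopsis, Protocol 10.1.2 and SAP 7.0 does give a CI for a mean difference. All of this stands. It means the intended rule can be inferred; it does not mean the rule is written down. Neither document pairs its inequality with a scale and sign that fit its declared endpoint.

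A reader might infer three stronger things that the documents do not support:

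- *That the SAP version will govern, so a worse product is likely to pass.* Nothing says the SAP prevails. SAP 8.0 says it was changed to follow the protocol, and the error in the other direction, rejecting equivalent products, is just as available from the printed text.
- *That the plan offers no valid interval.* Table 2 conflicts with the t-test option; it does not remove it.
- *That one-sided 0.025 was clearly intended.* The formulas imply one-sided 0.05, and the 95% CI is never called two-sided.

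**Conclusion.** The concern holds as a contradiction in the primary decision rule and must be fixed before unblinding. The opposite inequalities, the mismatch between the −5 margin and the declared score, the unnamed bound and the unresolved sidedness are all on the page. Applied literally to the declared endpoint, −5 gives a wrong decision with either inequality: far too lenient in the SAP form (0.84 against 0.025 at the margin) and close to impossible to meet in the protocol form (about 0.0003 for identical products). These probabilities rest on the Step 3 assumptions. They show what the wording permits and do not predict what the sponsor's analyst would do.

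**What to change.** Put one rule in Protocol 1.1, 3.4.2, 10.1.2 and 10.2.2 and in SAP 5.0 and 7.0:

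- ε = mean final-visit OSDI score, Nanodrop minus Systane Balance (higher is worse). H0: ε ≥ +5; H1: ε < +5. Non-inferiority is shown if the upper limit of the two-sided 95% CI for the mean difference is below +5.
- State that this is one-sided 0.025 and change alpha in the sample-size formula to match. If one-sided 0.05 is kept instead, say so and use that bound in both places.
- If reductions are preferred as the endpoint, declare that in Protocol 7.4.1 and SAP 6.0 and use H1: ε > −5, with the lower limit above −5.
- In Protocol Table 2, replace the Mann-Whitney entry for OSDI with this CI from the t-test route already in Protocol 10.1.2 and SAP 7.0. Mann-Whitney may stay as supportive.
- Correct the duplicate H0 label in Protocol 10.2.2, and state that the no-differences sentence in SAP 7.0 does not decide non-inferiority.

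The cost is wording only, with no added visits or data. Sample-size adequacy is a separate matter and this correction does not solve it. With Nanodrop 1.1 points worse and SD 17.1, power is Φ(3.9/SE − z): 0.21 at 51 and 0.25 at 63 per arm with the two-sided 95% CI, or 0.31 and 0.36 at one-sided 0.05.

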## 1.1 Synopsis

Title of the study: Phase I-II clinical study to compare the safety and efficacy of Nanodrop® versus Systane® Balance in the treatment of patients with dry eye	
Study number: SOPH176-1218/I-II	Creation date: December 11, 2018
Protocol version: 1.0	Version date: 11-dic.-18
Therapeutic indication: Lubricante ocular	Use: Ojo seco
Estimated duration of the study (from the first visit of the first patient to the preparation of the final report) : 11 meses	Development phase: I-II
Goals: Security: To evaluate the safety of ophthalmic application of Nanodrop® by quantifying the incidence of unexpected Adverse Events (AEs) related to the investigational product (IP).	
Effectiveness: To demonstrate the non-inferiority of Nanodrop® compared to Systane® Balance in the treatment efficacy of patients with dry eye, using the OSDI (Ocular Surface Disease Index) test score.	
Hypothesis: Security: $H_0$ = Nanodrop® is safe in its ophthalmic application, presenting an incidence of unexpected AEs, related to the PI less than 20% of the population of the Nanodrop® safety group $H_1$ = Nanodrop® is not safe for ophthalmic application, as it presents an incidence of unexpected AEs related to the PI greater than 20% of the population in the Nanodrop® safety group. Effectiveness: $H_0$ = Nanodrop® is inferior to Systane® Balance by more than 5 points on the OSDI test score $H_0: \mu_A - \mu_B > \delta$ $H_1$ = Nanodrop® is inferior to Systane® Balance by 5 points or less on the OSDI test score $H_1: \mu_A - \mu_B \leq \delta$	
Study design: Phase I-II, comparative, non-inferiority, active-controlled, parallel-group, double-blind, randomized clinical trial. Safety analysis is performed upon completion of the first 12 subjects in the Nanodrop® group. If fewer than 20% of unexpected adverse events (AEs) related to the investigational product occur, recruitment continues until the sample size for the efficacy analysis is complete.	
Number of subjects: n= 126 evaluable subjects 63 evaluable subjects per group (both eyes).	Main inclusion criteria: Diagnóstico de ojo seco
Selection criteria :	

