#### 10.1.4 Deviations from the statistical analysis plan

According to the sample size calculation to meet the efficacy objective, 102 evaluable subjects (51 subjects per arm) are required. If this number is not met due to a loss of subjects exceeding the 20% threshold established in this protocol (loss to follow-up or withdrawal from ICF), as mentioned in section 5.3.1, in order to balance the treatment groups, the sponsor may substitute these subjects.

The results obtained from the replaced subjects will continue to be used for safety analysis and will be part of the ITT.

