## 10.2 Sample size calculation

### 10.2.1 Number of subjects calculated

n= 126 evaluable subjects (both eyes)

63 subjects per arm.

An estimated 63 subjects (both eyes) are enrolled per treatment arm. During the safety phase, 24 subjects (12 from each group) will be recruited, and 102 will be recruited during the final phase, completing the sample of 126 required for the efficacy analysis.

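### The stated 101 subjects (51 per arm) do not follow from the plan's own formula and inputs, and power under those inputs is 21–64%, not 80%

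*SAP*

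**What the plan says.** Protocol 10.2.2 and SAP 5.0 give the same non-inferiority formula for two means, with z at 1 − alpha and an allocation ratio k. The inputs are alpha 0.05, a margin "of -5 points on the OSDI score", and, in the protocol's words, "With a power of 80" per cent. The expected effect is "a reduction in the OSDI score of 17.6 points for the placebo group at their final visit versus a reduction of 16.5 points", where the second figure belongs to the arm called treated. Protocol 10.2.2 gives 17.1 as sigma, the SD; SAP 5.0 prints the same number as delta: "Considering a δ of 17.1". SAP 7.0 sets 1:1 allocation.

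The result appears only in the SAP: "The estimated sample size was 101 subjects (51 subjects per arm), which was increased by 25" per cent for losses, giving 126. Protocol 10.1.4 says "102 evaluable subjects (51 subjects per arm) are required". Protocol 10.2.1 speaks of "completing the sample of 126 required for the efficacy analysis", and the synopsis calls all 63 per group evaluable.

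Protocol 10.1.2 and SAP 7.0 base non-inferiority on a 95% CI without saying whether it is one- or two-sided.

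**The concern.** The printed formula solves for n_B, the number in one arm, yet the stated 101 is a total. Even the most favourable sign of the expected difference needs about twice 51 per arm. Non-inferiority on the OSDI is the primary efficacy objective, and 80% power is the stated justification for enrolling 126 subjects. If the true power is far lower, a sponsor or ethics committee relying on 80% is misinformed about the chance of a conclusive answer, and a failure caused by low precision could be misread as evidence that the product is inferior.

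**Working it through.** **Inputs.** SD 17.1 (Protocol 10.2.2); margin 5 points; alpha 0.05 used one-sided, because the formula takes z at 1 − alpha (1.645); power 80% (z = 0.8416); k = 1 (SAP 7.0). Let d be the true difference, positive when the test product is better. The stated reductions differ by 17.6 − 16.5 = 1.1. Reading 'placebo' as the control and 'treated' as Nanodrop gives d = −1.1. This is a reading, since the trial has no placebo arm, so d = 0 and d = +1.1 are shown as well.

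**The plan's own figure.** The loss step reproduces: 101 × 1.25 = 126.25, so 126. The 101 does not. With k = 1 the factor (1 + 1/k) is 2, and the formula is

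n per arm = 2 × [17.1 × (z₁₋α + 0.8416) / (d + 5)]²

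| d | n per arm, alpha 0.05 | n per arm, alpha 0.025 (two-sided 95% CI) |
|---|---|---|
| +1.1 | 97.2 → 98 | 123.4 → 124 |
| 0 | 144.6 → 145 | 183.6 → 184 |
| −1.1 | 237.7 → 238 | 301.8 → 302 |

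None is 51. Two routes come close, both conjecture. A difference of +1.0 gives 100.4, so 101 *per arm*, which would fit a per-arm result taken as the total and then halved. Leaving out the factor 2 gives 50.2 at +1.0 (48.6 at +1.1). The documents state no difference of 1.0.

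**Power at the stated sizes.** Power = Φ((d + 5) / (17.1 × √(2/n)) − z₁₋α). For example, with n = 51 and d = +1.1 the standard error is 17.1 × √(2/51) = 3.386, 6.1 / 3.386 = 1.801, and Φ(1.801 − 1.645) = 0.562.

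| n per arm | Criterion | d = +1.1 | d = 0 | d = −1.1 |
|---|---|---|---|---|
| 51 | one-sided 0.05 | 56% | 43% | 31% |
| 63 | one-sided 0.05 | 64% | 50% | 36% |
| 51 | two-sided 95% CI | 44% | 31% | 21% |
| 63 | two-sided 95% CI | 52% | 37% | 25% |

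Noncentral-t values agree within one percentage point. The second term of the printed power equation adds at most 0.3 points.

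**Distance from the estimate to the bound.** This is t × 17.1 × √(2/n). With 51 per arm it is 5.62 (one-sided 95%) or 6.72 (two-sided 95%); with 63 per arm, 5.05 or 6.03. All exceed 5, so an observed difference of zero would fail. It would pass only if the observed SD were below 5 / (t × √(2/n)): 15.2 or 12.7 with 51 per arm, 16.9 or 14.2 with 63.

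**SD that would rescue the claim.** For 80% power at one-sided 0.05 the SD would have to be 12.4 / 10.2 / 7.9 with 51 per arm, or 13.8 / 11.3 / 8.8 with 63, for d = +1.1 / 0 / −1.1.

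**The case against.** The strongest defence is the phrase 'both eyes', which accompanies the sample size in both documents. Counting 102 eyes per arm as independent gives 82% power at one-sided 0.05 when d = +1.1, and 126 eyes give 88% (81% with a two-sided 95% CI). This does not stand. The size is stated in subjects, and the OSDI is one questionnaire score per subject (Protocol 7.4.4.1), so a second eye adds no observation. With d = −1.1, even counting eyes gives only 49–57%.

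A second objection is that the power figures are conditional. That is correct. The 17.1 accompanies reductions in OSDI, while the primary outcome is the day-29 score, and Protocol Table 2 assigns the OSDI a Mann-Whitney test while the formula compares means. The check shows that the stated size does not follow from the stated inputs; it does not establish the power the trial will actually have. A baseline-adjusted analysis could reduce the residual SD, but none is specified for the OSDI.

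Third, 21–64% spans unlike cases: its ends combine the least and the most favourable choices. At the formula's own alpha and the 51 evaluable per arm of Protocol 10.1.4, the range is 31–56%.

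Finally, 102 and 126 can be understood as a target and an enrolment number: Protocol 10.1.4 allows 20% loss, and 126 × 0.8 = 100.8. What remains is that the synopsis and 10.2.1 call all 126 evaluable or required. Likewise, delta for sigma in the SAP is a symbol slip that changes no result.

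**Conclusion.** The concern holds. Under the stated SD of 17.1, 5-point margin and alpha of 0.05, the plan's formula requires 98 to 238 evaluable subjects per arm for 80% power, against the stated 51. No subject-level reading reaches 80%. The best case, 64%, needs all 63 per arm analysable, a one-sided 95% bound and a true advantage of 1.1 points for the test product. It is generous, because the plan allows for losses and drops subjects below 70% adherence from the efficacy analysis. Which value within 21–64% applies depends on choices the documents leave open: the direction of the expected difference, the sidedness of the CI and the evaluable number. How 51 arose is not established, and the conclusion does not depend on it.

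**What to change.** In SAP 5.0 and Protocol 10.2.2 and 10.1.4:

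1. Label the formula's result as subjects per arm.
2. State the expected difference with a sign consistent with the margin, and say which group is meant by 'placebo' and by 'treated'.
3. In the SAP, correct the symbol for 17.1 from delta to sigma.
4. State whether the 95% CI is one- or two-sided, and use the matching alpha in the calculation.
5. Reconcile 102 evaluable (10.1.4) with 126 evaluable (synopsis, 10.2.1).

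If enrolment stays at 126, replace the 80% with the power that matches the chosen evaluable number, CI and assumed difference, taken from the power table above. Add that a CI containing both zero and the margin would be inconclusive; a CI lying wholly beyond the margin would show inferiority and should not be described that way.

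This costs wording and a less favourable stated power, with no extra subjects. Keeping 80% instead would need 98–238 evaluable per arm at one-sided 0.05, or 124–302 with a two-sided 95% CI, before any allowance for losses.
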